History of malignancy (non-metastatic and metastatic; excluding non- melanoma skin cancer)	Outcome: VTE risk factor	Defined as ≥1 ICD-10 diagnosis code for malignancy (excluding non-melanoma skin cancer) in the 12 months prior to or on the day of the index tofacitinib dispensing.
Age >50 years at tofacitinib initiation	Outcome: VTE risk factor	Defined as age at tofacitinib initiation >50 years.
History of diabetes	Outcome: VTE risk factor	Defined as $\geq 1$ ICD-10 diagnosis code for diabetes in the 12 months prior to or on the day of the index tofacitinib dispensing.
History of hypertension	Outcome: VTE risk factor	Defined as ≥1 ICD-10 diagnosis code for hypertension in the 12 months prior to or on the day of the index tofacitinib dispensing.
Initiating tofacitinib with ≥1 VTE risk factor	Outcome: VTE risk factor	Defined as ≥1 VTE risk factor (as listed and defined above) identified in the 12 months prior to or on the day of the index tofacitinib dispensing (unless otherwise specified).
Number of VTE risk factors identified prior to tofacitinib initiation	Outcome: VTE risk factor	Calculated as the sum of the number of VTE risk factors (as listed and defined above) identified in the 12 months prior to or on the day of the index tofacitinib dispensing (unless otherwise specified).

Table 3.	Operational	definitions of	f study	variables in	the selected	databases
----------	-------------	----------------	---------	--------------	--------------	-----------

Variable	Role	Operational definition
Number of UC patients with: ≥1 VTE risk factor; no prior alternative therapy (i.e., biologic); and an ADD >10 mg in Weeks 16-23, Weeks 24- 31, Weeks 32-39, and Weeks 40-47 of follow-up t	Outcome: VTE risk factor	Defined as a patient meeting all of the following criteria: ≥1 ICD-10 diagnosis code for UC; ≥1 VTE risk factor (as listed and defined above); 0 prescription medication dispensings for a biologic (as identified by ATC codes) in the 12 months prior to and including the date of the index tofacitinib prescription dispensing; and an ADD of >10 mg in Weeks 16-23, Weeks 24-31, Weeks 32- 39, and Weeks 40-47 of follow-up, respectively (ADD defined in Section 9.3.4). Complete list of biologics in ANNEX 6. LIST OF ATC CODES FOR MEDICATIONS OF INTEREST TO AVOID WHILE TAKING TOFACITINIB.

 Table 3.
 Operational definitions of study variables in the selected databases

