Assessment of VTE risk factors while receiving tofacitinib therapy (duration of tofacitinib therapy defined in Section 9.3.3)

VTE	Outcome: VTE risk factor	Defined as $\geq 1$ ICD-10 diagnosis code for VTE while receiving tofacitinib therapy.
Surgery, major	Outcome: VTE risk factor	Defined as $\geq 1$ procedure code for a major surgery while receiving tofacitinib therapy.
MI	Outcome: VTE risk factor	Defined as $\geq$ 1 ICD-10 diagnosis code for an MI while receiving tofacitinib therapy.
Heart failure	Outcome: VTE risk factor	Defined as $\geq$ 1 ICD-10 diagnosis code for heart failure while receiving tofacitinib therapy.
Use of combined hormonal contraceptives or hormonal replacement therapy	Outcome: VTE risk factor	Defined as ≥1 prescription dispensing of a combined hormonal contraceptives and/or hormonal replacement therapy (as identified by ATC codes) while receiving tofacitinib therapy.
Inherited coagulation disorder	Outcome: VTE risk factor	Defined as ≥1 ICD-10 diagnosis code for inherited coagulation disorder while receiving tofacitinib therapy.
Malignancy (non- metastatic and metastatic; excluding non-melanoma skin cancer)	Outcome: VTE risk factor	Defined as ≥1 ICD-10 diagnosis code for malignancy (excluding non-melanoma skin cancer) while receiving tofacitinib therapy.
Diabetes	Outcome: VTE risk factor	Defined as ≥1 ICD-10 diagnosis code for diabetes while receiving tofacitinib therapy.

Variable	Role	Operational definition
Hypertension	Outcome: VTE risk factor	Defined as ≥1 ICD-10 diagnosis code for hypertension while receiving tofacitinib therapy.
Discontinuation of tofacitinib after developing ≥1 VTE risk factors while taking tofacitinib	Outcome: VTE risk factor	Defined as ≥1 VTE risk factor while receiving tofacitinib therapy (as listed and defined above) PLUS 0 prescription dispensings for tofacitinib within a specific time window after the code for the VTE risk factor.
		Note: The time window for when to look for a tofacitinib prescription dispensing will be specific to the VTE risk factor acquired while receiving tofacitinib therapy and will be operationalized during SAP development.
		Duration of tofacitinib therapy defined in Section 9.3.3.

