		Complete list of biologics in ANNEX 6. LIST OF ATC CODES FOR MEDICATIONS OF INTEREST TO AVOID WHILE TAKING TOFACITINIB.
		Note: Patients have 6 months to discontinue tofacitinib to allow them time to be seen by their healthcare provider.
		Duration of tofacitinib therapy defined in Section 9.3.3.

 Table 3.
 Operational definitions of study variables in the selected databases

Variable	Role	Operational definition		
Appropriate continuation of tofacitinib for patients who turn 65 years old while receiving tofacitinib	Outcome: Age 65 years and older	Defined as patients aged 65 years, receiving tofacitinib, who have $\geq 1$ prescription dispensing of tofacitinib from the time they turn 65.5 years old through to the end of the follow-up period PLUS $\geq 1$ prescription dispensing for a biologic (as identified by ATC codes) prior to that tofacitinib prescription dispensing.		
		Complete list of biologics in ANNEX 6. LIST OF ATC CODES FOR MEDICATIONS OF INTEREST TO AVOID WHILE TAKING TOFACITINIB.		
		Note: Patients have 6 months to discontinue tofacitinib to allow them time to be seen by their healthcare provider.		
		Duration of tofacitinib therapy defined in Section 9.3.3.		
Analysis of CV risk factors	Analysis of CV risk factors in patients using tofacitinib w			
Assessment of CV risk factor 9.7.1.2.2.1.3 [Patients with	rs prior to initiation of tofacitinib (will CV risk factors])	be stratified by sex as outlined in Section		
Elderly at tofacitinib initiation (patients 65 years and older)	Outcome: CV risk factor	Calculated as the date of tofacitinib initiation minus the patient's year of birth and reported in the following categories: $<65$ years and $\ge 65$ years.		
Current or past smoker x	Outcome: CV risk factor	Defined as $\geq 1$ ICD-10 diagnosis code for tobacco use disorder or $\geq 1$ procedure code for counselling visits for smoking or $\geq 1$ prescription dispensing (as identified by ATC code[s]) for a nicotine replacement product in the 12 months prior to or on the day of the index tofacitinib dispensing.		
History of diabetes	Outcome: CV risk factor	Defined as ≥1 ICD-10 diagnosis code for diabetes in the 12 months prior to or on the day of the index tofacitinib dispensing.		

Table 3.Operational definitions of study	variables in the selected databases
--	-------------------------------------

<sup>w In GKV claims, outpatient diagnoses are reported quarterly.

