<sup>x Potential for very low sensitivity leading to misclassification. This variable will be reported if feasible.

Variable	Role	Operational definition
History of hypertension	Outcome: CV risk factor	Defined as $\geq 1$ ICD-10 diagnosis code for hypertension or $\geq 1$ prescription dispensing (as identified by ATC code[s]) for an antihypertensive in the 12 months prior to or on the day of the index tofacitinib dispensing.
		Complete list in ANNEX 8. LIST OF ATC CODES FOR ANTIHYPERTENSIVES.
History of hyperlipidaemia	Outcome: CV risk factor	Defined as $\geq 1$ ICD-10 diagnosis code for hyperlipidaemia or $\geq 1$ prescription dispensing (as identified by ATC code[s]) for a statin or other antihyperlipidaemic in the 12 months prior to or on the day of the index tofacitinib dispensing.
		Complete list in ANNEX 9. LIST OF ATC CODES FOR ANTIHYPERLIPIDAEMICS.
History of coronary artery disease (defined as MI, stroke, CABG [coronary artery bypass graft], or PCI [percutaneous coronary intervention])	Outcome: CV risk factor	Defined as $\geq 1$ ICD-10 diagnosis code for MI or stroke or $\geq 1$ procedure code for CABG or PCI in the 12 months prior to or on the day of the index tofacitinib dispensing.
History of chronic kidney disease	Outcome: CV risk factor	Defined as $\geq 1$ ICD-10 diagnosis code for chronic kidney disease in the 12 months prior to or on the day of the index tofacitinib dispensing.
History of stable angina pectoris	Outcome: CV risk factor	Defined as ≥1 ICD-10 diagnosis code for stable angina pectoris in the 12 months prior to or on the day of the index tofacitinib dispensing.
Initiating tofacitinib with $\geq 1$ CV risk factor	Outcome: CV risk factor	Defined as ≥1 CV risk factor (as listed and defined above) identified in the 12 months prior to or on the day of the index tofacitinib dispensing.

 Table 3.
 Operational definitions of study variables in the selected databases

Variable	Role	Operational definition

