# 9.4.1. Sweden: The National Patient Register, the Prescribed Drug Register, the Swedish Medical Birth Register, the National Cancer Registry, the Cause of Death Register

Health care in Sweden is primarily government-funded and managed at the national, regional, and local level. Only a small proportion of the population (6%) also have some type of supplementary private health insurance. In most regions, there is no formal gatekeeping and patients may contact specialists directly. In Sweden, patients with inflammatory rheumatic diseases like RA and UC are typically treated by hospital-based specialists as opposed to general practitioners (GPs). The current study will utilize four large Swedish registers linked via patients' personal identifications numbers: the NPR, the PDR, the Swedish Pregnancy Register, and the NCR.

The NPR includes information regarding inpatient and outpatient non-primary (i.e., specialist) encounters across Sweden; outpatient GP encounters are not captured in the NPR. Beginning in 1987, coverage for inpatient admissions became nationwide and is near 100%. Coverage for outpatient non-primary care began nationwide in 2001 and is around 87% (although it may be higher for somatic care such as rheumatology). Key variables include diagnosis, surgery, external causes of injury (E-codes), age, sex, hometown, hospital, specialty, and information related to hospital admissions and discharges (e.g., dates, main and contributory diagnoses, mode of discharge). Information on patient anthropometric data (e.g., height, weight, body mass index) is not available nor are laboratory test results (e.g., ALC, blood lipid levels) or clinical measurements (e.g., blood pressure). A number of diagnoses, including RA, have been reported to have high positive predictive values in the inpatient register; in recent studies, the reported positive predictive value in the NPR was 91% for RA and 79% for UC. The NPR is updated annually.

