The PDR, maintained by the National Board of Health and Welfare, contains all prescribed and dispensed medication for patients in Sweden. Coverage of prescriptions is close to 100%, however, inpatient administrations are not captured and there is only partial capture of drugs administered in hospital outpatient visits. Information included in the PDR include basic demographic characteristics such as age, sex, and residency, as well as medication-specific information such as the prescribed / dispensed drug (e.g., ATC code, International Non-proprietary Names [INN]), prescription dispensing date, pack size, dispensed amount, formulation, dosage, prescribing healthcare practitioner, and costs. The PDR is updated monthly. The Swedish MBR was established in 1973 and is managed by the National Board of Health and Welfare (NBHW). The register covers 100% of births and stillbirths of at least 22 gestational weeks since July 2008 (and of at least 28 gestational weeks before July 2008) in Sweden thereby facilitating the identification of tofacitinib exposure during pregnancy. There are no data on elective terminations or spontaneous abortions in the register. The register covers information such as gestational duration, self-reported smoking status during pregnancy, diagnoses during pregnancy, date of birth, delivery complications, diagnoses of the mother and the child, Apgar score, low birthweight, head circumference and survival. The data for the previous calendar year are usually available in December of the following year. Access to the register data for scientific research is decided by the NBHW through a standard application procedure and is assessed on a case-by-case basis.

The NCR was started in 1958 and is managed by the NBHW. The registry records all newly diagnosed tumours and blood cancers diagnosed by clinical, morphological, or other laboratory examinations, as well as cases diagnosed at autopsy. Since the mid-1980s, there are six regional registries associated with the oncological centres in each medical region of Sweden where the registration, coding, and major check-up and correction work is performed. The register includes information on patient characteristics, tumour characteristics, diagnosis, and date and cause of death. Data are updated on an annual basis with a lag time of approximately 13 months. Applications for data access are sent to the National Board of Health and Welfare and processed by a pre-defined data permit process.

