### 9.4.3. The Netherlands: The PHARMO Database Network

The PHARMO Database Network is a population-based network of electronic healthcare databases and combines anonymous data from different primary and secondary healthcare settings in the Netherlands. All electronic patient records in the PHARMO Database Network include information on age, sex, socioeconomic status, and mortality. The databases are linked on an annual basis, meaning that the average lag time of the data is approximately 1 year (the updated databases are available in the second half of the year). The PHARMO Database Network is broadly representative of the Dutch population and covers both primary and secondary (inpatient and outpatient) settings of care, as well as pharmacy (community and in-patient) dispensed treatments through its different databases.

The different databases in the network include:

- The General Practitioner Database captures electronic medical record (EMR) data from registered GPs (covering approximately 20% of the Dutch population). Key variables include diagnoses (coded via the International Classification of Primary Care [ICPC]), symptoms, laboratory tests and test results, referrals to specialists, and drug prescription information including type of product (ATC codes), prescription date, strength, dosage, regimen, quantity, and route of administration. Height, weight, tobacco use, and alcohol abuse information are also available.
- The Out-patient Pharmacy Database (covering approximately 25% of the Dutch population) includes data on all GP or specialist prescribed products, as well as hospital pharmacies. -The Outpatient Pharmacy Database captures drug dispensings from outpatient pharmacies. Key variables include product (ATC codes), dispensing date, strength, dosage regimen, quantity, route of administration, prescriber specialty, and costs.
- The In-patient Pharmacy Database captures inpatient medication administrations and drug dispensings from hospital pharmacies (covering approximately 10% of the Dutch

population). Key variables include drug type (ATC codes), start and end date of use, strength, dosage regimen, and route of administration.

- The Clinical Laboratory Database captures the results of laboratory tests requested by GPs and medical specialists (covering approximately 5% of the Dutch population). Key variables include date and time of testing, test result, unit of measurement, and type of clinical specimen.

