discretion of the healthcare provider will be limited. For example, assessment of whether tofacitinib is being "used with caution in patients with known risk factors for VTE, regardless of indication and dosage" cannot be done directly in this study. This assessment will be approximated using the number and proportion of patients who had VTE risk factors ( $\geq 1$  and  $\geq 2$ ) and were prescribed tofacitinib before and after the 2019 Article 20 referral aRMM materials were implemented. However, this assessment is limited in the sense that if the proportion of patients with VTE risk factors prescribed tofacitinib does not decline over time, it does not necessarily mean that prescribers were not prescribing tofacitinib with caution among patients with VTE risk factors.

The results from this study may not be generalizable to other member states of the EU (e.g., prescribing patterns and implementation of the recommended screenings and monitorings may vary by country). Finally, only the RA indication has received full reimbursement in Hungary (in May 2019), with the PsA and UC indications available only via the Named Patient Program. Thus, Hungary will not have a VTE Reporting Period 1 for any indication and also will not have a VTE Reporting Period 2 for the PsA and UC indications, nor will Hungary have a CV and Malignancy Reporting Period 1 or a CV and Malignancy Reporting Period 2 for the PsA and UC indications, which limits the MAH's ability to examine changes in the utilisation of tofacitinib among patients with VTE risk factors, among elderly patients, and among patients with CV or malignancy risk factors in Hungary following the updated recommendations and limitations for use. Additionally, there may be smaller patient numbers for these two indications relative to the RA indication in Hungary. However, there will be more comprehensive data across indications from Sweden. In the Netherlands, the PHARMO Database Network requires linkage between different data sources. As the same patients may not be captured by all databases and the initial number of tofacitinib patients is not high, patient counts may be affected by linkage.

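### Baseline hypertension needs a diagnosis code as a VTE risk factor but a code or a dispensing as a CV risk factor, and diabetes needs a code throughout; in Sweden code-only rules under-count both

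*Protocol*

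**What the plan says.** All the definitions are in Section 9.3.2, Table 3.

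- **Hypertension, VTE set, baseline:** at least one "ICD-10 diagnosis code for hypertension in the 12 months prior to or on the day of the index tofacitinib dispensing". There is no dispensing route.
- **Hypertension, VTE set, on treatment:** at least one "ICD-10 diagnosis code for hypertension while receiving tofacitinib therapy".
- **Hypertension, CV set, baseline:** a diagnosis code or at least one "prescription dispensing (as identified by ATC code[s]) for an antihypertensive in the 12 months prior" to, or on, the index day, using the Annex 8 list. The on-treatment CV rule also accepts a code or a dispensing.
- **Diabetes:** a code is required wherever it appears: as a comorbidity, in the VTE set and in the CV set. The baseline risk-factor wording is at least one "ICD-10 diagnosis code for diabetes in the 12 months prior to or on" the index day. Annexes 6 to 9 contain no list of glucose-lowering drugs.

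On the Swedish sources, Section 9.4.1 says that "outpatient GP encounters are not captured in the NPR". Of the Prescribed Drug Register it says "Coverage of prescriptions is close to 100" per cent.

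Section 9.9 explains that cautious use in patients with VTE risk factors cannot be observed directly: "This assessment will be approximated using the number and proportion of patients who had VTE risk factors", at the thresholds of one or more and two or more. Sections 9.7.1.2.2.1.1 and 9.7.1.3.1 also report each VTE factor separately and the number of factors per patient.

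**The concern.** Two rules for one condition, over one window and in one cohort, will give two hypertension proportions in the same report with nothing to explain the difference.

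In Sweden the narrower rule also depends on the weaker source. A patient whose hypertension or diabetes is managed only by a GP has no diagnosis code in the National Patient Register, yet dispensed treatment would appear in the drug register. Section 9.9 names this primary-care gap as a cause of misclassification for smoking, but not for hypertension or diabetes.

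The Swedish proportions for these two factors, and the count of VTE factors built on them, would be too low. Table 4 gives Sweden the largest expected cohort, about 3400 patients.

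**Working it through.** The plan states no figure on this point, so there is none to reproduce. The check compares the texts and then illustrates the size.

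**1. Can the two rules disagree, and in which direction?**

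| Baseline record in the 12 months | VTE rule | CV rule |
|---|---|---|
| Code, with or without a dispensing | hypertensive | hypertensive |
| Listed dispensing, no code | not hypertensive | hypertensive |
| Neither | not hypertensive | not hypertensive |

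The CV rule contains the VTE rule. Disagreement occurs only in the second row and always lowers the VTE figure.

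**2. Which outputs are exposed?**

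- The individual hypertension and diabetes proportions, and the sum of VTE factors, are exposed directly.
- The baseline VTE list includes age over 50, so the proportion with at least one factor is already met by everyone over 50. A missed condition changes it only in patients aged 50 or under with no other factor.
- The proportion with two or more factors (Section 9.9) is less protected. A patient over 50 whose only other factor is an uncoded hypertension drops from two to one.
- The on-treatment VTE list has no age item, so the denominators for continuing or discontinuing after developing a factor do not have that protection.

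**3. What does Annex 8 contain?** Every entry is a C02 code. Perindopril, ramipril, lisinopril, valsartan, amlodipine and indapamide, all named in Annex 7 as components of statin combinations, are not in Annex 8. As written, the CV dispensing route reaches only patients on C02 agents.

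**4. Illustrative size for hypertension.** Let p be the true prevalence among initiators, s the share of hypertensive patients with a register code in the window, and d the share of uncoded hypertensive patients with a listed dispensing. The documents give none of these; all are assumptions, and false positives are ignored.

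- VTE rule finds p × s.
- CV rule finds p × [s + (1 − s) × d].
- Gap = p × (1 − s) × d.

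With p = 30% and s = 50%, the VTE rule finds 0.30 × 0.50 = 15.0%. The CV rule finds:

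| d | CV rule | Gap (points) |
|---|---|---|
| 2% | 15.3% | 0.3 |
| 10% | 16.5% | 1.5 |
| 50% | 22.5% | 7.5 |
| 90% | 28.5% | 13.5 |

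Over p = 20–40%, s = 30–80% and d = 2–90%:

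- Smallest gap: 0.20 × 0.20 × 0.02 = 0.0008, or 0.1 points.
- Largest gap: 0.40 × 0.70 × 0.90 = 0.252, or 25.2 points.
- If a C02-only list is taken to mean d of at most 10% (also an assumption), the largest gap is 0.40 × 0.70 × 0.10 = 0.028, or 2.8 points.

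No comparable range is computed for diabetes. The mechanism is the same, at its own prevalence and coding share.

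**The case against.** **The algorithms are preliminary.** Section 9.3.2 leaves final algorithms and code lists to the SAP, and Section 9.9 admits diagnostic misclassification and a look-back that may be too short for chronic conditions. This stands as far as code lists go. But the protocol itself fixes two rules for one condition, a SAP that follows Table 3 would reproduce both, and the general caveat explains neither rule.

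**The diabetes rule is consistent.** This is correct: there is no contradiction for diabetes. The point there is avoidable under-capture in Sweden, where a nearly complete dispensing source is already in the study.

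**Copying the CV rule may recover little.** This stands while Annex 8 holds only C02 codes, and it is why the list must be reviewed first.

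**A dispensing route on treatment would count refills as new disease.** This also stands. A long-treated patient's routine refill would register as a factor developed on tofacitinib and inflate those denominators. The existing on-treatment CV rule has the same weakness.

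**Stronger readings that the documents do not support.**

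- A reader might infer that the rule invalidates comparisons between countries. Section 9.7.1 rules out pooling and comparative analysis because recording and coding differ, and the period comparisons are made within a country under one rule.
- A reader might take the Section 9.9 remark about more comprehensive data from Sweden as a claim about risk-factor capture. It concerns indications, in contrast with Hungary's missing PsA and UC periods.
- A reader might infer that the response to the VTE warnings is judged only by these proportions. Section 9.3.1 also lists the UC dose outcome, discontinuation and continuation.
- A reader might take the code-plus-therapy diabetes example in Section 9.9 as the adopted definition. It is only an example of limiting rule-out diagnoses.

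**Conclusion.** The point holds in a limited form. Table 3 gives baseline hypertension two unexplained definitions, so an uncoded patient with a listed dispensing can be classified differently in the VTE and CV tables. It would go too far to say that patients are generally discordant: only that one group is.

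In Sweden, code-only rules under-count hypertension and diabetes in the individual VTE proportions and in the number of VTE factors, provided that some initiators are managed for these conditions only in primary care. The proportion with at least one factor is affected mainly at age 50 or under.

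The size cannot be derived from the documents. The range of 0.1 to about 25 points for hypertension rests wholly on the assumed p, s and d, and a C02-only list puts it at the low end. A large shortfall should not be quoted as a finding. The case for changing the plan is the inconsistency and the availability of a better source.

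**What to change.** 1. At baseline, use one hypertension rule in the VTE and CV sets: at least one ICD-10 code or at least one antihypertensive dispensing. Review Annex 8 first, since it lists only C02 codes.
2. Define baseline diabetes in every set as at least one ICD-10 code or at least one glucose-lowering dispensing, and add the ATC list.
3. Report the ICD-10-only version of both conditions as a sensitivity row.
4. On treatment, count a dispensing as a newly developed factor only if the patient had neither a code nor a dispensing for that condition at baseline, so that refills are not counted.
5. Extend the Swedish primary-care limitation in Section 9.9 from smoking to hypertension and diabetes.

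**Cost:** Table 3 wording, one revised and one new code list, a sensitivity row and a sentence in Section 9.9. Dispensing records are already part of the planned sources, and the CV hypertension rule already uses them. The downside is some loss of specificity, because some of these drugs are dispensed for other conditions. The plan already accepts that kind of loss for CV hypertension, but a wider Annex 8 would increase it, and the sensitivity row shows how far the results depend on it.
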